- **Leuprolide acetate** – A subset of premenopausal women will receive GnRH_{AG} (leuprolide acetate) 3.75 mg/mo by intramuscular injection every 4 weeks for 24 weeks (6 doses).
 - Contraindications for use include: hypersensitivity to GnRH, GnRH agonist analogs or any of the excipients in Lupron Depot; undiagnosed vaginal bleeding; known or suspected pregnancy; lactation.
 - In women who are pregnant, use of leuprolide acetate may cause fetal abnormalities.
 - Leuprolide acetate may cause an anaphylactic reaction in volunteers with hypersensitivity to GnRH.
 - Regular menstruation should stop during leuprolide acetate therapy but spotting or breakthrough bleeding may occur. Cessation of menses does not ensure that pregnancy will not occur. Normal menstrual function is usually restored within 2-3 months after therapy is discontinued.
 - Leuprolide acetate may cause symptoms related to hypoestrogenism including hot flashes, headaches, nausea, emotional lability, decreased libido, acne, myalgia, sleep disorders, reduction in breast size, hypertension, and vaginal dryness. Bone loss may occur, although the amount lost over the 24-week intervention should be recovered slowly after discontinuation of leuprolide acetate treatment. There may be a development or worsening of depression and the occurrence of memory disorders
 - In rare cases, leuprolide acetate may cause seizures (post-marketing concern).
 - Leuprolide acetate therapy for 24 weeks may cause an increase in FM (~1.0-1.5 kg), a decrease in fat-free mass (1-1.5 kg), an increase in total, LDL, and HDL cholesterol (5-10%), and an increase in triglycerides (15-20%).
 - Local injection site reactions including induration and abscess may occur.
- **Risk of radiation exposure:** Participants will be exposed to radiation during the PET/CT and DXA scans. During the PET/CT scans, participants are exposed to radiation from the CT and from the radiopharmaceuticals. The primary risk of this level of radiation exposure is to the unborn fetus of pregnant women. All participants will perform one DXA and PET/CT study, and a subset of premenopausal women will perform these tests twice. The estimated radiation exposure during each study visit is listed in the table below

Table 2. Estimated radiation exposure (mSv)

Visit #	C-11	F-18	CT	DXA
0				0.015
1	0.91		0.96	
2	0.91	3.5	0.96	
			2.55	
8				0.015
8	0.91		0.96	
9	0.91	3.5	0.96	
			2.55	

- During the DXA scans, the radiation exposure is approximately 0.015 mSv per total body

scan.

- During study visit #1 (room temperature), participants will be exposed to approximately 1.87 mSv of radiation.
- During study visit #2 (cold exposure), participants will be exposed to approximately 7.92 mSv of radiation.
- After allowing for 20% extra exposure from the procedures, women who complete study visits #1 and #2 will be exposed to a total of up to 11 mSv or radiation (~3.6 cross-country flights). Pre-menopausal women who complete study visits #8 and 9 will be exposed to a total of up to 22 mSv of radiation (7.3 cross-country flights). This is below the annual amount of exposure for radiation workers (50 mSv).

FDG will accumulate in the bladder. The estimated whole body radiation exposure following the FDG infusion depends on when subjects void. Participants will be instructed to void 1 hour after the FDG infusion. Please note that the cold exposure will induce diuresis, and in our experience, subjects void immediately after the procedures. The void volume will also be larger than what might be seen at room temperature, and this increases elimination of the radiopharmaceuticals

- *PET/CT*: Aside from the radiation exposure, the risks associated with the PET/CT scan are the chance of incidental findings. PET/CT is used to diagnose a few diseases like some cancers and diseases of the brain. There is a very small risk that diseases like this may be found. Some participants may also experience claustrophobia in the scanner. Some participants may experience a burning sensation in the arm during the ^{11}C -acetate infusion. The infusion only lasts for a few seconds and the burning sensation quickly diminishes after the infusion is complete.
- *sEMG and skin temperature sensors*: The sEMG and temperature sensors may cause some minor discomfort and/or skin irritation due to the paste used to attach the sensors.
- *Core temperature pills*: The temperature pill moves through the intestinal tract like food does, but on rare occasions, can become stuck in the intestines.
- *Venipuncture and IV catheters*: Venipuncture will be performed to obtain blood samples for laboratory analyses, and an IV catheter will be used during the ^{11}C -acetate and ^{18}FDG infusion. There is a small risk of syncope, local hematoma, infection, and thrombosis associated with intravenous blood sampling.
- *Confidentiality and privacy*: The use of questionnaires, interviews, and collection of personal medical information poses a risk to confidentiality and privacy and may cause embarrassment.

Plans to minimize risks

Leuprolide acetate: The risks associated with use of the study drugs will be minimized by enrolling participants who do not have contraindications for their use. Volunteers will undergo a medical history and physical examination by a study clinician. Absence of pregnancy (urine test) will be confirmed before GnRH_{AG} injections are administered. Participants will be observed for 30 min after drug injection to monitor for new hypersensitivity reactions. Women will be instructed that they should not become pregnant while taking study drugs because of risks to the fetus. This physician will discuss non-hormonal based contraceptive methods during the health and physical examination. They will be instructed that cessation of menses may or may not occur during the study and that cessation of menses does not provide protection against pregnancy; contraception (not hormonal) must be used.

Women who do not tolerate GnRH_{AG} therapy in the proposed study can refuse further treatment after each monthly dosing. Among the first 94 women treated with GnRH_{AG} in our previous and ongoing studies (R01 AG018198, P50 HD073063), this occurred only once. Participants will also meet with the study research nurse practitioner, providing a regular mechanism by which adverse events will be queried. A health status questionnaire will be used to track changes in use of medications (prescription and over-the-counter) or health (e.g., doctor visits, hospitalizations), as well as any study-related problems/concerns over the past 4 weeks. Participants will also complete e Menopausal Symptom List (MSL) to monitor the frequency and severity of menopause-related symptoms (e.g., hot flashes, depressed feelings); the Eating Behavior Questionnaire (EBQ) to monitor dietary restraint, disinhibition,

and hunger;⁷⁸ and the Pittsburgh Sleep Quality Index (PSQI) to monitor sleeping behavior.¹² After completing the study, Participants will be asked to notify study team when menstrual cycles have resumed. The study team will follow up after 2 months if no contact has been made by participant.

Radiation exposure: All participants will perform one DXA and PET/CT study, and a subset of premenopausal women will perform these tests twice. Women who complete study visits #1 and #2 will be exposed to a total 9.91 mSv or radiation. Pre-menopausal women who complete study visits #8 and 9 will be exposed to 19.61 mSv of radiation.

- To minimize risk to an unborn fetus, participants must have a negative pregnancy test prior to each measurement.
- DXA: Conducting two scans before and after the intervention involves a total radiation exposure of approximately 0.43 mSv, which is <1% of the annual allowable exposure for radiation workers (50 mSv/yr over **a 40 year career**).
- PET/CT: The FDA **annual** allowable exposure for radiation workers for whole body or organ specific radiation exposure is 50 mSv/yr **over a 40 year career**. Radiation exposure increases the risk of a fatal cancer by 4-5% per Sievert. Radiation exposure in this study is <50 mSv, so the increased risk is <0.001%. The highest organ radiation exposure in this study will be in the bladder. Conducting two studies before and after the intervention in the subset of premenopausal women will involve a total radiation exposure of 38 mSv in the bladder, which is ~76% of the **annual** allowable exposure. To minimize exposure, participants will void 30 min. after the FDG infusion, and then again as soon as the study is completed (2 hrs. after ¹⁸FDG administration). In our experience the cold exposure causes all participants to void by the time the study is completed. According to the Institute for Science and International Security, the average annual dose equivalent of natural ionizing radiation in Denver is 11.8 mSv/yr. In comparison to natural background radiation, the radiation exposure in the proposed experiments is comparable to 1.6 years of natural radiation from living in Denver.

Incidental findings during the PET/CT scans: All images for this study will be de-identified and reviewed for incidental findings. Should anything significant be found, the Nuclear Medicine physician will discuss these findings with the study MD. The participant will be contacted immediately by the Nuclear Medicine physician and advised on clinical follow-up to confirm findings.

Venipuncture and IV catheter: The risks of hematoma and infection are minimized by having trained personnel perform the procedures using sterile techniques.

Core temperature pills: Participants will be advised to avoid having an MRI test for at least a week after the study. Because the capsule is a radiotransmitter, participants will also be advised to avoid travel on commercial airlines for at least a week after the study. The recording device is electrically isolated and complies with hospital standards for electrical safety.

sEMG and skin temperature sensors: Any skin irritation from the sensors is expected to be minor and temporary.

Confidentiality and privacy: These risks will be minimized by not including personal identifying information on the forms, when possible, and by conducting interviews and collection of personal information in a private setting.

Evaluation of study-related events – The subset of premenopausal women enrolled in the intervention study will meet with a study clinician every 4 weeks to review a Health Status Questionnaire that the participants will complete. The questionnaire queries about changes over the past 4 weeks in medications, health status, and any concerns with study medications. The clinician will specifically note on the form whether there are any concerns that are possibly, probably, or definitely related to the study. Participants will also be instructed to report concerns that may be study related when they occur to the research nurse practitioner, [name], who will initiate event reports for both the programmed and spontaneous complaints.

E. Potential Scientific Problems:

We considered studying women across the menstrual cycle, rather than a cross-sectional comparison of pre- vs. postmenopausal women. The strength of the cross-sectional design is that postmenopausal

women will have been estrogen deficient for several years, which should maximize the attenuation of E₂ deficiency on BAT activity. A limitation is that we will not be able to determine whether this is also partially due to age. However, if the exploratory aim confirms that GnRH_{AG} reduces BAT activity, this will support the overall hypothesis that E₂ deficiency, rather than age, is the primary factor contributing to reduced BAT in postmenopausal women.

There is no known way to distinguish the energy expenditure associated with shivering and non-shivering thermogenesis in humans. Thus, we will employ rigorous techniques to measure shivering during cold exposure using both sEMG and ¹⁸FDG uptake into deep muscles. These data will be used to quantify shivering and used to interpret differences and changes in CIT.

Postmenopausal women will likely have higher levels of body fat, and body fat may increase in premenopausal women after GnRH_{AG}. As described above, the cooling suit delivers an identical cold stimulus during each study. Our intent is not to determine the maximal activity of BAT, but rather, determine if differences in BAT activation in response to a constant stimulus is either different between pre- and postmenopausal women (**SA2**), or changes after GnRH_{AG} (**SA3**). To account for differences or changes in body composition, REE will be expressed per kg of fat free mass.

We acknowledge that GnRH_{AG} causes a more abrupt withdrawal of ovarian function (i.e., weeks rather than years) and does not generate the same gonadotropin response of menopause (i.e., low rather than high). However, the GnRH_{AG} model is also a strength because it allows us to control the sex hormone environment in a manner that is not possible when studying the natural menopause transition.

F. Data Analysis Plan:

Sample size justification and power analyses – Sample size calculations and power analyses were performed using SAS 9.4 (SAS Institute, Inc., Cary, NC). For our estimate of effect size, we refer to our previous study that measured CIT in the follicular and luteal phases (Figure 5).⁸ In that study, CIT was higher during the luteal phase ($2530 \pm 524 \text{ kcal} \cdot \text{d}^{-1}$ vs. $2225 \pm 440 \text{ kcal} \cdot \text{d}^{-1}$). Unfortunately, we did not measure BAT activity. Because there were no differences in shivering in this study, we will assume differences in CIT were due to differences in NST; we also assume that this reflects differences in BAT activity. Using a pooled SD of 484 kcal/d, 32 evaluable participants per group (64 total) will provide 80% power to detect a difference of 305 kcal/d in CIT between pre- and postmenopausal women using a 2-sided t-test and a type I error rate at 0.05. Assuming a dropout rate of 15%, 38 participants per group will need to be enrolled to yield the desired sample size of 64 participants. The primary endpoint is BAT oxidative metabolism (¹¹C clearance rate, expressed per mL of BAT per s⁻¹). In our previous study of 12 men, BAT oxidative metabolism increased during cold exposure from 0.35 ± 0.13 to 0.74 ± 0.19 (mean \pm SEM).⁶ Using a pooled SD of 0.45, we estimate that we will have 80.0% power to detect a difference between groups of 0.32 during thermoneutral conditions. Using a pooled SD of 0.66, we will have 84.7% power to detect a difference between groups of 0.50 during cold exposure. In another study, BAT oxidative metabolism at room temperature was 0.35 in lean men vs. 0.05 in overweight men with T2D.¹⁰ We have also reported that BAT oxidative metabolism increased in lean men from 0.73 to 1.59 following a 4-week cold acclimation.⁷ Thus, we consider this to be a meaningful effect size to examine differences in BAT oxidative metabolism between groups during thermoneutral conditions and during cold exposure. A secondary endpoint is BAT activity volume. In our previous study, BAT activity volume was $57 \pm 16 \text{ ml}$ (mean \pm SE).⁶ Using a pooled SD of 55 ml, the study will have 80.0% power to detect a difference of 39 mL between groups. In another study, we reported that BAT activity volume was 48 vs. 4 ml in young healthy men compared to older men with T2DM.⁵ Thus, we consider this to be a meaningful effect size.

Analysis strategy - Statistical analyses will be performed using SAS 9.4. Analyses will begin with descriptive plots of individual variables to evaluate distributional characteristics and for quality assurance. The effect of menopausal status on each endpoint will be estimated using a linear regression model. The endpoint will be the response variable and a variable indicating menopausal status will be the explanatory variable (equivalent to a 2-sample t-test). If a variable that is related to the response variable is not balanced between menopausal groups, that variable will be included in the regression model to eliminate the potential of the effect of menopausal status being confounded by that variable. For all multivariable analyses, regression diagnostics will be used to ensure that the group of explanatory variables are not collinear. Secondary analyses will be performed to investigate whether REE is associated with either BAT

oxidative metabolism or BAT activity volume. Exploratory analyses will investigate the changes in BAT oxidative metabolism and BAT volume of activity associated with GnRH_{AG} treatment (Aim 3) Because these aims are exploratory, results will be reported using descriptive statistics, mean change, and 95% confidence intervals (CIs) for the changes in the primary and secondary endpoints.

G. Summarize Knowledge to be Gained:

The importance of understanding mechanisms that contribute to risk for obesity cannot be overstated given the current epidemic of overweight and obesity in the U.S. and other developed countries worldwide. Although the loss of ovarian function is only one of a multitude of physiological, behavioral, and environmental factors that increase risk for fat gain, it is potentially a very important one in women. The strong evidence from multiple large RCTs and smaller physiologic trials indicates that estrogen-based HRT attenuates weight gain in postmenopausal women by an average of 40%. Further, in the absence of HRT, weight gain in postmenopausal women is accompanied by a disproportionate increase in abdominal fat. Although abdominal obesity and the related metabolic dysfunction increases risk for coronary artery disease in both women and men, the risk of mortality may be ~5-fold higher in women. Also, it has been estimated that abdominal obesity and metabolic dysfunction account for about 20% of coronary events in men, but 48% of events in women. Such statistics underscore the importance of understanding the mechanisms of abdominal fat gain in women – including both energy expenditure and energy intake regulation. In this context, the proposed study has the potential to reveal a consequence of the loss of ovarian function that has widespread health implications.

H. References:

4. [name] B, Labbe SM, Turcotte E, [name] F, Richard D, [name] AC. A critical appraisal of brown adipose tissue metabolism in humans. *Clin lipidology* 2015;10:259-80.
5. [name] DP, Labbe SM, Noll C, Kunach M, Phoenix S, Guerin B, Turcotte EE, [name] F, Richard D, [name] AC. Selective Impairment of Glucose but Not Fatty Acid or Oxidative Metabolism in Brown Adipose Tissue of Subjects With Type 2 Diabetes. *Diabetes* 2015;64:2388-97.

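### The stated fatal-cancer risk from study radiation (<0.001%) is about 40 to 100 times lower than the protocol's own coefficient and doses give, and several dose totals do not reconcile with Table 2

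*Combined protocol and SAP*

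**What the plan says.** The radiation figures appear in two parts of Section IV.D.

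- **Potential risks, including Table 2.** Doses are listed by visit and source. The text repeats the first visit's sum: "During study visit #1 (room temperature), participants will be exposed to approximately 1.87 mSv of radiation". The cold visit is put at 7.92 mSv, and each DXA at 0.015 mSv. Maxima follow, with a margin described as "After allowing for 20% extra exposure from the procedures". On that basis, those completing Visits 1 and 2 "will be exposed to a total of up to 11 mSv", while the figure for women who repeat the scans is up to 22 mSv.
- **Plans to minimize risks, radiation exposure.** For Visits 1 and 2, women "will be exposed to a total 9.91 mSv or radiation". For those who repeat the scans the total is 19.61 mSv. DXA before and after the intervention is put at about 0.43 mSv. The risk coefficient is "Radiation exposure increases the risk of a fatal cancer by 4-5% per Sievert", and the conclusion drawn from it is "Radiation exposure in this study is <50 mSv, so the increased risk is <0.001", with a percent sign after the last figure.

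The radiation text numbers the repeat scans as Visits 8 and 9, whereas Table 1 numbers them 9 and 10. Below they are called the second round.

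**The concern.** The coefficient, the dose bound and the conclusion stand side by side, and the conclusion cannot be obtained from the other two. Fifty mSv is one twentieth of a sievert, so 4-5% per sievert cannot shrink to a thousandth of a percent.

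This is the only numerical fatal-cancer risk in the protocol. It is in the section an ethics board uses to weigh risk, and it applies to every woman enrolled, all of them healthy volunteers. The *Potential risks* text names the fetus as the main concern at this level of exposure, so the participant's own cancer risk rests on this one number. The error is in the reassuring direction and is largest for women scanned twice. The maxima also appear to fall short of the allowance they claim to include.

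**Working it through.** **Inputs, all from Section IV.D.** Table 2, in mSv: C-11 0.91 per injection; F-18 3.5; regional CT 0.96; whole-body CT 2.55; DXA 0.015. Risk coefficient: 0.04-0.05 per Sv.

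**Step 1. Reproduce the dose figures.**
- Visit 1: 0.91 + 0.96 = 1.87 mSv. Agrees with the text.
- Visit 2: 0.91 + 3.5 + 0.96 + 2.55 = 7.92 mSv. Agrees with the text.
- One round: 1.87 + 7.92 = 9.79 mSv, or 9.805 with one DXA. The text says 9.91, which does not agree.
- Two rounds with DXA: 2 × 9.805 = 19.61 mSv. Agrees with the text, so the 9.91 and 19.61 totals rest on different sums.

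**Step 2. Try to reproduce the risk.** Risk (%) = dose in Sv × coefficient × 100.

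| Dose | Risk at 4% per Sv | Risk at 5% per Sv | Multiple of 0.001% |
|---|---|---|---|
| 9.805 mSv, one round | 0.039% | 0.049% | 39-49 |
| 19.61 mSv, two rounds | 0.078% | 0.098% | 78-98 |
| 11 mSv, stated maximum | 0.044% | 0.055% | 44-55 |
| 22 mSv, stated maximum | 0.088% | 0.110% | 88-110 |
| 50 mSv, bound in the sentence | 0.20% | 0.25% | 200-250 |

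Using 9.79 mSv for one round leaves the first row unchanged to the digits shown. No row gives <0.001%. The last row tests the sentence against its own premise; it does not describe a planned exposure.

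**Step 3. Work backwards.** A risk of 0.001% is 0.00001. Dividing by 0.05 and 0.04 per Sv gives 0.20 and 0.25 mSv. One C-11 injection is 0.91 mSv. The same paragraph compares study exposure with about 1.6 years of Denver background at 11.8 mSv per year (19.61 / 11.8 = 1.66). At that rate, 0.20-0.25 mSv is about 6 to 8 days.

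**Step 4. A possible source.** 0.01961 × 0.05 = 0.00098, just under 0.001. A proportion may have been printed with a percent sign. This is inference. Even as a proportion, 0.001 does not follow from a 50 mSv bound, which gives 0.0020-0.0025.

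**Step 5. The 20% allowance.**
- One round: 9.79 × 1.2 = 11.75; 9.805 × 1.2 = 11.77 mSv (stated maximum 11).
- Two rounds: 19.61 × 1.2 = 23.53 mSv (stated maximum 22).
- Allowance actually included: 11 / 9.805 = 1.12 and 22 / 19.61 = 1.12, that is about 12%.
- Risk with the full allowance: 0.047-0.059% at 11.77 mSv and 0.094-0.118% at 23.53 mSv.

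**Step 6. DXA.** At 0.015 mSv per scan, two scans give 0.03 mSv and four give 0.06 mSv. The text says 0.43.

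**The case against.** The risk percentage has no good defence. No other part of the protocol corrects it, and no choice of planned dose or rounding yields <0.001%. The fair objections concern the rest.

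- **The 20% base is not defined.** Applied to CT alone (4.47 mSv per round), 20% gives 10.7 and 21.4 mSv. Applied to tracers alone (5.32 mSv), it gives 10.9 and 21.7. Either fits maxima of 11 and 22. The protocol states neither restriction, and the plain reading is 20% of the total. The mismatch therefore stands as something to reconcile, but it is small: about 0.75 and 1.5 mSv.
- **DXA.** The 0.015 mSv is per total-body scan, and DXA also measures spine and hip density. Regional scans might account for 0.43, but the protocol does not say so, and Table 2 carries only 0.015 per DXA visit. This mismatch overstates dose if Table 2 is complete.
- **9.91 versus 9.805** is a difference of about 1% and has no practical effect.
- **Importance.** Doses by visit, the worker limit, the bladder dose and a background comparison are all disclosed, so the wrong percentage is not the only risk information. Absolute risk is about 0.1% or less at planned doses. Consent pages are not available here, so whether participants saw <0.001% is unknown.

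These points limit the weight of the secondary items. They leave the main error untouched.

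**Conclusion.** The concern holds. On the protocol's own inputs the stated risk is too low by a factor of 39-49 for one round of scans and 78-98 for two. The 200-250-fold figure at 50 mSv shows only that the sentence contradicts its premise.

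The result assumes risk proportional to dose, as a per-sievert coefficient implies, and takes the coefficient and Table 2 as given; neither was checked against outside sources. If both percentages are read as relative increases, the factors are the same.

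The secondary discrepancies (the 20% maxima, 9.91 mSv and 0.43 mSv) are real on the plain text but minor. The need for correction rests on the risk figure. Sample size, power and analysis are unaffected.

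**What to change.** 1. Replace the risk sentence with figures derived from the stated coefficient: about 0.04-0.05% for Visits 1 and 2 and about 0.08-0.10% for women who complete both rounds. If maximum doses are quoted, give the risk at those doses too. With 20% on the Table 2 totals this is about 0.047-0.059% and 0.094-0.118%. If the 50 mSv bound is kept, the matching statement is below 0.25%.
2. Reconcile the totals with Table 2: 9.91 against 9.79 or 9.805 mSv; 11 and 22 against 11.75-11.77 and 23.5 mSv, or state what the 20% applies to; and 0.43 mSv for DXA against 0.015 mSv per scan, or state which scans it covers.
3. Carry the corrected figures into any participant-facing text that repeats them.

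The cost is a text amendment and a less favourable stated risk. No procedure changes.
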